 - If they decide to initiate PrEP, they will be prescribed PrEP medications by a physician in accordance with routine clinical care at their local PrEP clinic in the community.

Title: Linking High-Risk Jail Detainees to HIV pre-exposure Prophylaxis: PrEP-LINK

PI: [name]

Site: University of Arkansas for Medical Sciences

Only participants who test negative for HIV on their rapid test will be eligible to participate in the study. Individuals in the jail with a preliminary positive HIV test result will be immediately referred to the jail medical division, operated by TurnKey, Inc. for confirmatory testing.

Individuals tested in the community will be immediately referred to the Arkansas Department of Health for confirmatory testing.

- A baseline assessment survey (SEE: PrEP-LINK Baseline Battery) to be used during all 3 data collection time points (baseline, 6-month and 12-month)
 - The baseline assessment survey will ask questions about education, job status, criminal justice history, substance use, sexual behaviors, and other behaviors which may put individuals at risk for HIV, in addition to questions on knowledge and interest in PrEP.
 - The baseline assessment survey includes the following measures and it to be used in both **Specific Aims 2 & 3**:

Measure Name	Citation	Baseline Battery Page Number	Notes
PrEP-LINK Cover Sheet	Compiled for this study by the PIs	1	For internal tracking purposes
Demographics	Compiled for this study by the PIs	2-5	
Criminal Justice Involvement History	Compiled for this study by the PIs	5-6	
Health Insurance	Compiled for this study by the PIs	6	
HIV Sex Risk Perception	Compiled for this study by the PIs	7	
Income (ASI Lite)	McLellan, A.T., Luborsky, L., O'Brien, C.P. & Woody, G.E. (1980). An improved diagnostic instrument for substance abuse patients: The Addiction Severity Index. Journal of Nervous & Mental Diseases , 168, 26-33	8-9	
PrEP Knowledge (PrEP Knowledge Scale, RADAR)	Parsons, J. T., Rendina, H. J., Lassiter, J. M., Whitfield, T. H., Starks, T. J., & Grov, C. (2017). Uptake of HIV pre-exposure prophylaxis (PrEP) in a national cohort of gay and bisexual men in the United States: the motivational PrEP cascade. Journal of acquired immune deficiency syndromes (1999), 74(3), 285.	10	

Title: Linking High-Risk Jail Detainees to HIV pre-exposure Prophylaxis: PrEP-LINK
 PI: [name]
 Site: University of Arkansas for Medical Sciences

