Measures. The primary intervention measures, including common measure across both studies are provided above in the description of Aim 2. As part of Aim 3, data will be collected at all follow-up time points (3, 6 and 12 months) by the study RA. Additional measures are provided below.

Additional Secondary Measures for Aim 3

1) PrEP adherence. Self-reported PrEP adherence will supplement clinical chart abstraction. An assessment of the optimal period for self-reported antiretroviral adherence (using electronic monitoring data as the standard for predictive validity) found that longer time periods (e.g., 30 days versus 4 days) were more accurate for assessing adherence than shorter time periods.⁵¹ Therefore, we will use adherence over a 30-day period as self-reported adherence outcome.

Title: Linking High-Risk Jail Detainees to HIV pre-exposure Prophylaxis: PrEP-LINK

PI: [name]

Site: University of Arkansas for Medical Sciences

2) HIV risk behaviors/behavioral adjustment. Participants' HIV-transmission risk behaviors will be assessed with the TCU HIV/AIDS Risk Assessment, which is designed specifically for CJ-involved individuals,⁵² at all three data collection time points. We will collect more detailed data on sexual behaviors, including number of sexual partners, sexual activities, and condom use based on EXPLORE study measures. These measures are valid and reliable among high-risk men.⁵³

3) Substance use. Participants' alcohol use will be measured with the Alcohol Use Disorders Identification Test - Consumption (AUDIT-C) and the Addiction Severity Index - Lite (ASI-Lite), both of which have been validated for use with diverse populations (e.g., African American, Hispanic/Latino, and White).⁵⁶

Data analysis. Data analysis will focus on the feasibility, acceptability, and preliminary efficacy of the PrEP-LINK pilot intervention.

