The preliminary efficacy of the intervention will be determined by assessing the primary outcome of PrEP uptake by looking at the medical charts of the participants. A secondary outcome will be PrEP adherence defined by participants who were adherent to the medication determined by self-report at 3, 6, and 12 months. Following intent-to-treat (ITT) principles, all

Title: Linking High-Risk Jail Detainees to HIV pre-exposure Prophylaxis: PrEP-LINK

PI: [name]

Site: University of Arkansas for Medical Sciences

randomized participants will be included in data analyses. Standard bivariate analytic techniques, such as Spearman rank-order correlations, odds ratios, and Fisher's exact tests, will be used to assess preliminary associations between the intervention and each measure of PrEP uptake and to identify factors associated with the outcomes. Generalized linear regression models will be informed by these bivariate analyses.

In addition, we will test the randomization process by comparing the baseline demographic and confounding variables of the participants in each arm with Fisher's exact test for dichotomous variables, chi-square tests for nominal variables, *t*-tests for normally distributed continuous variables, and Wilcoxon signed-rank tests for non-normally distributed continuous variables, with statistical significance determined at alpha ≤ 0.05 . Any variable for which randomization does not result in equal proportions in each arm will be incorporated into the multiple-regression models as a potential confounding variable. Attrition effects will be evaluated by testing whether systematic differences exist between those participants who complete the research versus those who drop out. Thus, we can determine any potential bias introduced by attrition from the study.

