The primary analysis will compare uptake of PrEP by looking at the medical charts of the participants and self-reported behaviors of PrEP usage at the 3, 6, and 12 month visits between the study arms. Changes in self-reported adherence (verification with clinical chart abstraction, including lab tests for serum levels of medications), sexual behavior adjustment, post-incarceration contextual variables, and substance use will also be examined. Moreover, group differences in PrEP uptake, time-to-uptake, and number of PrEP clinic appointments kept will be compared. All analyses will use two-tailed tests of significance, with significance at alpha = 0.05. We will use generalized linear models with properly chosen link functions to analyze longitudinal data for each study aim. These models will be estimated with generalized estimating equations that use robust standard error estimates^{57,58}; they provide an extension of regression analysis to the case of correlated or repeated observations and allow for the inclusion of categorical and count-dependent variables and for appropriate modeling of covariance structures when observations are correlated across time.

Power Calculations. Because this is a pilot study, the primary emphasis will be on the acceptability and feasibility of the two arms; hence, power is limited to determine efficacy of the intervention. We used GPower⁵⁹ software to estimate the difference in proportions between the two groups, with respect to PrEP-LINKage, that could be detected with 80% power. Given 40 participants per group (total $n = 80$), one-tailed alpha = .05, and a proportion of 0.5 for the control group, we will have 80% power to detect a 0.26 difference in proportions between groups.

Ethical Considerations

This study will be conducted in accordance with all applicable government regulations and University of Arkansas for Medical Sciences research policies and procedures. This protocol and any amendments will be submitted and approved by the UAMS Institutional Review Board (IRB) to conduct the study.

Title: Linking High-Risk Jail Detainees to HIV pre-exposure Prophylaxis: PrEP-LINK

PI: [name]

Site: University of Arkansas for Medical Sciences

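### The sexual-behaviour and substance-use comparisons do not name the outcome's own baseline value as a covariate, although it is collected

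*Combined protocol and SAP*

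**What the plan says.** The primary-analysis paragraph of Data Analysis sets the target for the behavioural measures. The sentence opens with changes in self-reported adherence and then lists the rest: "sexual behavior adjustment, post-incarceration contextual variables, and substance use will also be examined". It gives no contrast, time point or dependent variable. The method follows in the same paragraph: "We will use generalized linear models with properly chosen link functions to analyze longitudinal data for each study aim", estimated by GEE with robust standard errors. These models are said to "allow for the inclusion of categorical and count-dependent variables".

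The only rule on covariates is in the preceding paragraph, on testing the randomisation: "Any variable for which randomization does not result in equal proportions in each arm will be incorporated into the multiple-regression models". Such variables are treated as possible confounders.

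On data collection, Study Design and Procedures describes the baseline battery as "to be used during all 3 data collection time points (baseline, 6-month and 12-month"). Its table of measures includes the TCU HIV risk tool, AUDIT and ASI-Lite. Additional Secondary Measures for Aim 3 places the TCU tool "at all three data collection time points" and names AUDIT-C and ASI-Lite for substance use. It also adds more detailed sexual-behaviour items based on EXPLORE, without stating when they are collected.

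**The concern.** In a randomised comparison of a measure taken before and after assignment, the participant's own baseline is usually the most useful covariate. Here it is collected but has no planned role. Three analyses fit the wording without using it as a covariate:

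- a difference between arms in change from baseline;
- a GEE with baseline as one of the repeated responses and an unconstrained arm-by-time term, which with complete data gives the same contrast as change;
- a comparison of follow-up values alone.

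For a continuous outcome, none of these is more precise in large samples than the baseline-adjusted comparison, and some are clearly less precise. The imbalance rule does not fill the gap. It makes adjustment depend on a chance finding, so the same outcome could be adjusted in one realisation of the trial and not in another.

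At stake is the precision of secondary comparisons on HIV risk and substance use, in a small pilot meant to inform a larger multi-site trial.

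**Working it through.** **The plan's own figure.** No precision or power figure is given for these outcomes. The only one, in Power Calculations, concerns PrEP linkage: 40 per group, one-tailed 0.05, control proportion 0.5, 80% power for a difference of 0.26. A pooled-variance calculation gives 78.6%, and the difference that gives exactly 80% is 0.265, so the statement reproduces to rounding. Only the 40 per group is used below.

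**Inputs**
- n = 40 per arm (Power Calculations).
- Two-sided alpha 0.05 (Data Analysis makes all tests two-tailed); 80% power.
- r, the correlation of baseline with follow-up: not in the documents, assumed 0.2 to 0.9.
- k, the baseline SD divided by the follow-up SD: not in the documents, taken as 1 and then 0.5.

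**Formulas.** With the follow-up SD set to 1, the variance of the arm contrast is proportional to:
- change: 1 + k² − 2rk, which is 2(1 − r) at k = 1;
- follow-up only: 1;
- baseline-adjusted: 1 − r².

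The ratio of change to adjusted is (1 + k² − 2rk)/(1 − r²) = 1 + (k − r)²/(1 − r²). At k = 1 this is 2/(1 + r). It is never below 1 and equals 1 only when k = r.

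**Variance relative to the baseline-adjusted contrast**

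| r | Change, k = 1 | Change, k = 0.5 | Follow-up only |
|---|---|---|---|
| 0.2 | 2/1.2 = 1.67 | 1.05/0.96 = 1.09 | 1/0.96 = 1.04 |
| 0.5 | 2/1.5 = 1.33 | 0.75/0.75 = 1.00 | 1/0.75 = 1.33 |
| 0.7 | 2/1.7 = 1.18 | 0.55/0.51 = 1.08 | 1/0.51 = 1.96 |
| 0.9 | 2/1.9 = 1.05 | 0.35/0.19 = 1.84 | 1/0.19 = 5.26 |

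A baseline less variable than follow-up therefore shrinks the ratio at low and moderate r, but not at every r. Change is less precise than ignoring baseline when r < k/2, that is, r < 0.5 at k = 1.

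**Detectable difference at k = 1**, in follow-up SDs: (1.960 + 0.842) × √(2V/40) = 0.626 × √V, where V is the variance above.

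| r | Change | Adjusted |
|---|---|---|
| 0.2 | 0.626 × √1.60 = 0.79 | 0.626 × √0.96 = 0.61 |
| 0.5 | 0.626 × √1.00 = 0.63 | 0.626 × √0.75 = 0.54 |
| 0.7 | 0.626 × √0.60 = 0.49 | 0.626 × √0.51 = 0.45 |
| 0.9 | 0.626 × √0.20 = 0.28 | 0.626 × √0.19 = 0.27 |

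**Check.** A simulation at 40 per arm (4,000 runs, k = 1) gave variances for change and adjusted of 1.40 and 0.93 at r = 0.3, 0.99 and 0.73 at 0.5, and 0.58 and 0.51 at 0.7. The formulas give 1.40 and 0.91, 1.00 and 0.75, and 0.60 and 0.51.

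**Arm size.** The variance ratios do not depend on n. Study Population's 100 completers cover Aims 2 and 3 together, so 50 per arm would be too many. Taking Aim 3's share pro rata gives 110 × 100/120 = 92, or about 46 per arm.

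**The case against.** The strongest objection is that the plan never names a change score. A reader might infer from the word changes that baseline will be subtracted, but the documents do not support that. The named method is a longitudinal GEE, which could carry baseline as a covariate. The same word also governs self-reported adherence, which cannot be a baseline-subtracted score for anyone not on PrEP at entry. It may mean no more than course over time. This stands, and the point is therefore about an unstated role for baseline, not about a wrong method chosen.

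The size is also open to challenge. The ratios of 1.67 and 1.33 need equal SDs and an assumed r. The TCU tool is listed with a 30-day label, and participants are in jail or within 30 days of release. If that label is the recall window, the baseline answers may describe custody. That could lower r, which raises the ratio, or lower the baseline SD, which at moderate r reduces it. The documents settle neither. This stands too, which is why a range is shown.

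Three further limits are accepted:
- The guarantee of no loss of precision is a large-sample result for linear models. With a logit link, adding baseline changes the estimand to a conditional one and can increase its standard error.
- A baseline for the EXPLORE-based items is not established.
- These are secondary measures in a pilot whose stated emphasis is acceptability and feasibility.

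None of this supplies a reason to leave baseline adjustment to an imbalance test.

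**Conclusion.** The point holds as an improvement to the plan. The baseline values of the TCU, AUDIT/AUDIT-C and ASI-Lite measures are collected, no planned model uses them as covariates, and the one covariate rule would bring them in only by chance.

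If changes were contrasted, the variance would be 1.05 to 1.67 times that of the adjusted contrast for r from 0.9 down to 0.2. This assumes a continuous outcome and equal SDs. With a baseline SD half the follow-up SD, the excess is 9% at r = 0.2 and nil at r = 0.5. If follow-up alone were compared, the loss would run the other way, small at low r and large at high r. Prespecified adjustment protects against both.

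The consequence is minor. It concerns secondary behavioural outcomes and leaves the PrEP-uptake comparison untouched. It is not a finding that the plan uses an invalid analysis.

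**What to change.** Add to Data Analysis: for the TCU HIV-risk, AUDIT/AUDIT-C and ASI-Lite outcomes, and for the EXPLORE-based items where a baseline exists, the 6- and 12-month values will be modelled by GEE with arm, visit and arm-by-visit. The participant's baseline value of the same measure will be a prespecified covariate, whatever the baseline comparison of arms shows. The adjusted arm difference will be reported at each visit, and within-arm change will be descriptive only. Month 3 is left out because the follow-up schedule makes it a locator contact.

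At the same time, state whether the EXPLORE-based items are asked at baseline, and whether AUDIT or AUDIT-C is the analysed score.

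The cost is small but not nil: one parameter per outcome, a rule for a missing baseline value, and, where a logit link is used, a statement that the effect is conditional on baseline. For the battery measures no new data are needed.

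### The plan leaves open which uptake comparison is primary (source, horizon and model contrast), so testing each at 0.05 does not fix the uptake false-positive rate; naming one comparison is a cheap improvement

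*Combined protocol and SAP*

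**What the plan says.** The outcome summary after the aims lists PrEP uptake as a primary outcome, beside acceptability and feasibility. The Data Analysis section then describes the uptake comparison in several ways:

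- The preliminary-efficacy paragraph takes the "primary outcome of PrEP uptake by looking at the medical charts of the participants", with no time horizon. It plans bivariate techniques, Fisher's exact test among them, for "preliminary associations between the intervention and each measure of PrEP uptake".
- The primary-analysis paragraph adds a second source and three time points: charts together with "self-reported behaviors of PrEP usage at the 3, 6, and 12 month visits between the study arms".
- The same paragraph says that "group differences in PrEP uptake, time-to-uptake, and number of PrEP clinic appointments kept will be compared".
- One significance rule covers everything: "All analyses will use two-tailed tests of significance, with significance at alpha = 0.05".
- Generalized linear models are planned for the longitudinal data: "These models will be estimated with generalized estimating equations that use robust standard error estimates". No treatment contrast is named, whether an overall arm effect, an arm-by-time term or the difference at one visit.

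The power statement is for one difference between two proportions, with no source or horizon attached. In Study Design and Procedures, the survey battery is "to be used during all 3 data collection time points (baseline, 6-month and 12-month"), and the 3-month contact is a locator check-in.

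**The concern.** When a primary outcome has several admissible comparisons and each is tested at 0.05, the error rate for a claim that the intervention raised uptake is not 0.05 unless one comparison is fixed in advance. Here source, horizon and model contrast are all open. An analyst could follow the plan faithfully and still choose among results after seeing them. The results are meant to inform a multi-site trial. An effect taken from the most favourable visit or source would tend to be too large, and the arms are small.

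**Working it through.** **1. The plan's own figure.** Inputs from Power Calculations: 40 per group, control proportion 0.50, difference 0.26 (so 0.76), one-tailed alpha 0.05.

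- Mean proportion (0.50 + 0.76)/2 = 0.63.
- Null SE = √(2 × 0.63 × 0.37/40) = 0.1080.
- Alternative SE = √((0.50 × 0.50 + 0.76 × 0.24)/40) = 0.1040.
- Power = Φ((0.26 − 1.645 × 0.1080)/0.1040) = 78.6%, close to the stated 80%.

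The figure reproduces as one comparison of two proportions. It is one-tailed, while the analyses are two-tailed. With 1.96 in place of 1.645, power is 67.9% at 40 per arm and 81.5% at 55 per arm (the planned 110 for Aim 3, assuming equal allocation).

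**2. Three separate visit tests of nominal size.** If independent: 1 − 0.95³ = 14.3%. Tests on the same people are correlated, which lowers this. The documents give no correlation, so a range is shown, from simulation of the largest of three correlated normal statistics:

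| Common correlation (assumed) | Any of three at two-sided 0.05 |
|---|---|
| 0.3 | 13.6% |
| 0.5 | 12.5% |
| 0.7 | 10.8% |
| 0.8 | 9.8% |
| 0.9 | 8.3% |

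For cumulative uptake p(s) at an earlier and p(t) at a later visit, the correlation is √[p(s)(1 − p(t)) / (p(t)(1 − p(s)))]. Assumed uptake of 20%, 35% and 50% gives 0.68, 0.50 and 0.73, and 11.3% overall. Other assumed patterns: 40/45/50% gives 8.7%, 30/40/50% gives 10.1%, 10/30/50% gives 12.3%.

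**3. The same looks with Fisher's exact test.** This is the test the plan names that suits two proportions. Simulated null trials with 40 or 55 per arm and the same four uptake patterns give 5.1% to 7.1% for any of three looks. A single 12-month Fisher test gives 2.8% to 3.4%. Three looks therefore about double the single-test error, but from a conservative base.

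**4. Two visits only (6 and 12 months).** Tests of nominal size: 7.0% (correlation 0.9) to 9.8% (independent, 1 − 0.95²). Fisher's test: about 4% to 5%.

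**5. Both sources at three visits.** Six tests of nominal size, with a correlation between sources of 0.5 to 0.9 (assumed), give about 14% to 22%. With Fisher's test for both sources plus a log-rank test of time-to-uptake, the result is about 9% to 11%, assuming that 15% of self-reports are unrelated to the chart.

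**6. One prespecified contrast** from the longitudinal model: nominally 5%.

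**The case against.** A reader might infer that the plan runs at a false-positive rate of about 11%, or that any single significant visit counts as success. The documents support neither.

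- They give no uptake by visit and no correlation, so 11% is one point on an assumed scale. They never say that each visit is tested on its own.
- The longitudinal model is stated directly after the significance rule. Its natural use is to put the visits into one analysis, and one prespecified arm contrast would have nominal 5% error. That stands as far as it goes, but no contrast is named, so the model does not settle the choice.
- Fisher's exact test is named, and with it three chart looks stay near 5% to 7%. That stands for the three looks alone. It does not cover the wider set once self-report and time-to-uptake are tested too, and the list of techniques is given as examples only.
- Self-report at 3 months has no scheduled survey. A 3-month look would have to come from chart start dates, so the self-report comparison is effectively a two-visit one.
- The study is a pilot. Power Calculations puts the emphasis on acceptability and feasibility and concedes limited power for efficacy. The only numerical thresholds, above 80%, are for feasibility and acceptability; none depends on an uptake test. Appointments kept is closer to retention, a secondary outcome, than to uptake. This lowers the weight of the point but does not remove it, because uptake is still a primary outcome tested for significance.

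**Conclusion.** The point holds in a conditional form, as a cheap improvement of modest weight. The plan names no primary source, horizon or model contrast for a primary outcome and has no multiplicity rule, so its 0.05 standard does not by itself hold uptake false positives at 5%. The size depends on the open choices:

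- about 8% to 14% for three separate visit tests of nominal size;
- about 5% to 7% for three Fisher tests, against about 3% for one;
- higher if charts and self-report are both tested;
- nominally 5% for one prespecified contrast.

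The multiple-test figures assume that any one positive result would be reported as an uptake effect. Every figure that uses a correlation or uptake by visit rests on assumed values. No single rate can be attributed to the plan as written.

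**What to change.** Name one primary efficacy comparison: chart-recorded PrEP start within 12 months of randomisation, among all randomised Aim 3 participants. Report it as a risk difference by arm with a 95% confidence interval and one two-sided test at 0.05. This fits the 12-month chart collection, which records when PrEP was first taken, and the intent-to-treat statement. Say how a participant with no clinic record is counted.

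State that the power figure refers to this comparison, and restate it two-sided (67.9% at 40 per arm, 81.5% at 55, for 0.50 against 0.76).

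Report the 3- and 6-month looks, self-reported use, time-to-uptake, appointments kept and the longitudinal model as supportive, with confidence intervals and no significance claim. Reconcile the 3-month self-report comparison with the assessment schedule.

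The cost is wording only: no new data, visits or participants. The downside is that an early-visit difference can no longer be claimed as significant on its own. Keeping all three visits as primary with a Bonferroni split (0.05/3 = 0.0167) would cost more: power for 0.50 against 0.76 would be 50.6% at 40 per arm and 67.2% at 55.

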Primary outcomes will include acceptability and feasibility of the intervention, as well as PrEP uptake. Secondary outcomes will include adherence and retention in PrEP-related medical care at three, six and 12 months. Results will inform a subsequent multi-site RCT to test efficacy of the intervention in improving PrEP uptake, adherence, and retention in care among transitioning out of jail.

Between study aims 2 & 3 a total of 120 subjects will be consented with approximately 10 for aim 2 and 110 for aim 3.

NOTE: For this IRB application, we are only seeking approval for activities related to AIMs 2-3. AIM 1 was addressed in IRB #207297.

Study Design and Procedures

Human Subjects Involvement, Characteristics, and Design: Given the scope of inquiry and proposed project's aims, criminal justice (CJ) involved individuals are the human subjects of this project. Our research team understands that CJ-involved individuals represent a vulnerable population, as the correctional setting may be perceived as a coercive environment. Therefore, all research must be conducted with rigorous ethical standards and with numerous safeguards in place to protect participants. A 2006 Institute of Medicine report on research involving prisoners called for the following requirements:

- 1) a risk-benefit approach, whereby the potential benefits of the research to the prisoners outweigh the potential risks;
- 2) research should be conducted with "collaborative responsibility," referring to the idea that the design and implementation of the research should include the input of all relevant parties (including prisoners and correctional administrators);
- 3) voluntary informed consent must be obtained, and privacy maximized; and

Title: Linking High-Risk Jail Detainees to HIV pre-exposure Prophylaxis: PrEP-LINK

PI: [name]

Site: University of Arkansas for Medical Sciences

4) research must be monitored throughout the course of the study in order to verify compliance with approved protocols and to detect and report adverse events. The research plan described in this application complies with all of these requirements. Below each aim and the relevant human participants' involvement, characteristics and design are described.

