Maintaining Contact. Because the study will take place over about 12 months after the participant's enrollment date, it will be important for us to be able to keep in contact with them. During each visit, we will ask for information that will help us contact them in the community in order to schedule study related appointments. We will ask for many ways to try to reach the participant's in case their phone number is disconnected or changed. We will contact them regularly to update your contact information. Participants will be considered to have missed a 6 or 12 month assessment 60 days after the target assessment date, and will be eligible 30 days before target assessment date. Research staff will make at least 3 contact attempts to reach participants for the 3 month and 9 month locator check in, with the goal of updating contact information.

Study Population

Participants will be enrolled in the proposed PrEP-LINK intervention who are HIV-uninfected and detained in the Pulaski County jail or individuals who are within 30 days of having been released from a correctional setting. We will work with jail staff to identify individuals who are within 2 weeks of discharge and will conduct screenings among these individuals to determine study eligibility. We will also work with Central Arkansas Community Corrections and local re-entry centers to identify individuals who have been released from incarceration within 30 days. Because many types of HIV related risks are present in this population (e.g. MSM or PWID), we will recruit participants from the following groups: MSM, PWID and heterosexual non-substance users (more participants may be enrolled, as needed). For the final two categories, (PWID and heterosexuals), we will recruit equal numbers of men and women. The recruitment will be completed when 120 individuals have been consented to have 100 participants complete the protocol.

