The feasibility of the intervention will be determined by the proportion of participants who are screened, enrolled, and subsequently complete the PrEP-LINK intervention. To determine the feasibility of conducting an RCT, we will track the number of jail-involved individuals who express interest in the study and who are determined eligible for participation. Among these, we will calculate the percentages of those who reported being interested who were actually eligible; the number eligible who were successfully recruited and consented; randomized; and assessed at baseline, 3, 6, and 12 months (enrollment and completion of study related activities for >80% will indicate study feasibility). We will relay in individual detainees self-reporting in interest in participating in the study in the following ways. Firstly, the study CHW will be conducting weekly educational sessions. At the end of these sessions, individuals can disclose through an evaluation form whether or not they are interested in the study and if they are, a member of the study team will set up a follow up appointment to assess eligibility. The second way is direct referrals from the medical staff who may, with the permission of the detainee, make a referral to the study for eligibility assessment. The third method of recruitment will be through local Community Corrections facilities and re-entry centers. The study CHW will hold educational sessions at the recruitment sites (either in person or over Zoom for safety during the Covid-19 pandemic) where she will inform people about the study and conduct eligibility screeners with those who are interested, with the help of the research team.

The acceptability of the intervention will be determined with descriptive statistics of the participants' acceptability ratings, including whether they think the intervention is acceptable. Acceptability is define as > 80% of participants expressing high satisfaction with the intervention based on the Client Satisfaction Questionnaire - Revised. We will also review data collected by the study staff about time spent on the intervention and the ease of following the research and intervention protocols.

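### The only power figure is one-tailed on 80 participants, but the plan makes every test two-tailed and never gives the number to be analysed in Aim 3

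*Combined protocol and SAP*

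**What the plan says.** All references are to the combined protocol and SAP.

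- **Data Analysis, paragraph on the primary analysis:** "All analyses will use two-tailed tests of significance, with significance at alpha = 0.05". No exception is made for PrEP uptake or any other outcome.
- **Data Analysis, Power Calculations:** with 40 per group (80 in total), "one-tailed alpha = .05, and a proportion of 0.5 for the control group, we will have 80% power to detect a 0.26 difference". This is the only power statement in the document. The same paragraph says that, because the study is a pilot, the emphasis is on acceptability and feasibility; "hence, power is limited to determine efficacy of the intervention".
- **End of Specific Aims:** "a total of 120 subjects will be consented with approximately 10 for aim 2 and 110 for aim 3".
- **Study Population:** "The recruitment will be completed when 120 individuals have been consented to have 100 participants complete the protocol". Aims 2 and 3 are not separated here.
- **Data Analysis, preliminary efficacy:** under intention to treat, all "randomized participants will be included in data analyses". Fisher's exact test is listed among several example bivariate techniques.
- **Data Analysis, longitudinal models:** "These models will be estimated with generalized estimating equations that use robust standard error estimates".
- **Random Assignment to Study Condition:** assignment happens once a person has qualified, so consented and randomised are not the same count.

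**The concern.** Two things do not fit together. First, the power claim uses a one-tailed test at 0.05, which puts twice as much alpha in the direction of interest as the two-tailed rule set out one paragraph earlier. Second, its total of 80 matches neither the 110 consented for Aim 3, nor the 100 completers, nor the 120 consented over both aims.

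The two mismatches pull in opposite directions. Moving to two tails lowers power. Moving from 80 to a larger analysed number raises it. The stated 80% for a difference of 0.26 could therefore be too high or about right for the trial as planned, and the text does not let the reader decide.

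PrEP uptake is one of the primary outcomes, it has a planned between-arm comparison, and the results are meant to inform a later multi-site RCT. Its planners would naturally read 0.26 as this pilot's sensitivity under its own analysis rule.

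**Working it through.** **Inputs.** From Power Calculations: control proportion p1 = 0.50, difference d = 0.26, so p2 = 0.76; equal arms; n = 40 per arm. From the analysis rule: two-tailed alpha 0.05.

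**Formula.** Two-proportion z-test with pooled variance under the null:

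power = Φ[(d√n − z_α·s0) / s1]

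where s0 = √(2·p̄(1 − p̄)) with p̄ = 0.63, giving s0 = 0.6828, and s1 = √(0.50·0.50 + 0.76·0.24) = √0.4324 = 0.6576. The unpooled version puts s1 in place of s0.

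**Step 1: the plan's own figure.** One-tailed, z_α = 1.645, n = 40, d√n = 1.644:

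- pooled: (1.644 − 1.645·0.6828)/0.6576 = 0.793, power 78.6%
- unpooled: power 80.4%

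The stated 80% reproduces on its declared inputs. It is not a calculation slip.

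**Step 2: the same 80 participants under the planned rule.** Two-tailed, z_α = 1.960:

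- pooled: (1.644 − 1.960·0.6828)/0.6576 = 0.466, power 67.9%
- unpooled: power 70.6%

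The difference detectable with 80% power at n = 40 per arm becomes 0.295 (pooled) or 0.286 (unpooled).

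**Step 3: the number needed for 0.26 at 80% power.** n per arm = [(z_α·s0 + 0.842·s1)/d]²:

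- one-tailed, pooled: 41.6, so 42 per arm, 84 in total
- two-tailed, pooled: 52.9, so 53 per arm, 106 in total
- two-tailed, unpooled: 50.2, so 51 per arm, 102 in total

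**Step 4: two-tailed power over the analysed numbers the documents suggest.** The plan does not state the Aim 3 analysed number, so every row after the first is an assumption.

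| Analysed | Basis | Power for 0.26, pooled z | Detectable at 80%, pooled z |
|---|---|---|---|
| 80 | the power paragraph's own n | 68% | 0.295 |
| 88 | 80% of 110, borrowing the feasibility threshold | 72% | 0.283 |
| 92 | 110 × 100/120 = 91.7, rounded to equal arms | 74% | 0.277 |
| 100 | the completer target, taken as all Aim 3 | 78% | 0.267 |
| 110 | all Aim 3 consented are randomised and analysed | 82% | 0.255 |

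**Step 5: sensitivity to the test.** If Fisher's exact test were chosen for uptake, two-tailed power by full binomial enumeration at the same five sizes would be 60%, 65%, 67%, 71% and 76%. It first passes 80% at 61 per arm (122 in total). This is conditional, because the plan does not make Fisher's test the primary one.

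**The case against.** The strongest reply has four parts.

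*It is a pilot that says its power is limited.* This is true, and it keeps the consequence small. No decision rule or enrolment target rests on the 0.26. But a general caveat does not make a specific figure match the planned test.

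*No shortfall is shown.* This stands. With 110 analysed, two-tailed power is 82% and the claim is met. Uptake is read from medical charts and all randomised participants are to be analysed, so a missed survey need not remove anyone. Against that, 110 is a count of consented people, randomisation comes later, and the primary comparison also uses self-report.

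*The 106 depends on the formula.* This also stands in part. The unpooled z-test matches the stated 80% more closely (80.4%) and needs 102; at 100 analysed it gives 79.8% power and a detectable difference of 0.26. The fair statement is 102 to 106 by z-test. Every variant needs well over 80, so none of them rescues the figure at the plan's own n.

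*The 88 and 92 rows and the Fisher figures are speculative.* They are assumptions. The 88 row borrows a threshold meant for something else, "enrollment and completion of study related activities for >80% will indicate study feasibility", which is not a retention forecast. The Fisher results apply only if that test is chosen. The conclusion needs neither.

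**Conclusion.** The point holds, as an inconsistency and not an arithmetic error. The document's only power figure belongs to a one-tailed test that its own analysis rule excludes, and to a sample size that appears nowhere else in the plan. At that n of 80, the two-tailed rule gives 68% power by the pooled z-test (71% unpooled) instead of 80%. Between 102 and 106 analysed participants are needed for the stated property. Whether the trial as planned would meet it is undetermined: pooled z-test power runs from 68% at 80 to 82% at 110.

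These figures rest on control uptake of 0.50 and equal allocation, both taken from the power sentence, and on a single comparison of two proportions. The practical weight is modest given the pilot's stated emphasis, but the sentence is wrong as written and should be corrected.

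**What to change.** Delete the one-tailed, n = 80 figure and restate power at two-tailed 0.05 for the intended Aim 3 analysed number. For the new sentence to be checkable, it should also:

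1. name the test or model used for PrEP uptake;
2. give the number to be randomised in Aim 3 and the allocation ratio;
3. say whether the analysed number is all randomised or completers, with the attrition assumed;
4. show the range.

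The sponsor supplies items 1 to 3; they fill in missing detail. An example of item 4, with its numbers as assumptions:

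> Assuming 1:1 allocation and control uptake of 0.50, a two-tailed 0.05 pooled z-test has 80% power for a difference of 0.28 with 88 analysed, 0.27 with 100 and 0.26 with 110.

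If another test is chosen, its own figures should replace these; with Fisher's exact test the detectable differences at 88, 100 and 110 would be 0.30, 0.28 and 0.27.

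The cost is one rewritten sentence, with no extra participants and no change in procedures. The downside is a slightly less favourable figure if fewer than about 102 to 106 are analysed: by pooled z-test, 0.27 to 0.28 at 100 to 88 analysed, and 0.295 if the number really is 80.
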